Shift tables of maximum grade compared to baseline tabulated according to the FDA guidance: Toxicity Grading Scale for Healthy Adult and Adolescent Volunteers Enrolled in Preventive Vaccine Clinical Trials, or in accordance with the normal ranges of the clinical laboratory (below, within, or above normal range) for parameters for which no toxicity grades are defined.

A listing of clinical laboratory test results outside the reference ranges will be provided.

Vital Signs

Vital sign results and change from baseline results will be summarized by timepoint using descriptive statistics.

Limited Physical Examination

Abnormal findings in physical examination will be listed.

Pregnancy

A listing of pregnant subjects will be displayed.

Additional Analyses (descriptive only; p-values are descriptive and not corrected for multiple testing)

Immunogenicity

Serum antibody, mucosal antibody and cellular immune response will be summarized using descriptive statistics by sampling timepoint for all subjects and by baseline values.

Seroconversion rates will be presented by timepoint and by baseline starting values.

Vaccine virus detection

Viral shedding will be summarized using descriptive statistics.

Additional (exploratory) endpoints may be analyzed.

Sample size

The sample size of 50 subjects per group was chosen based on reports of studies of other vaccines in early stage development. This study is not powered for any formal comparisons.

Subject Characteristics Data Set

Demographics will include by-treatment summaries of age, height, weight, BMI, race, and gender.

Other baseline characteristics may be summarized.

Analysis Datasets

The Safety set will include any subject who receives at least one administration of IP.

The full analysis set (FAS) will include all subjects randomized, received IP and had at least one post baseline assessment.

If necessary, a per protocol set (PPS) will include all subjects in the FAS with no major protocol violations or deviations.

Issue Date (Version) 18May2020 (v8.0)

LIST OF ABBREVIATIONS AND DEFINITIONS OF TERMS

List of Abbreviations

ACIP	Advisory Committee on Immunization Practices
AE	adverse event
BMI	body mass index
CDC	Centers for Disease Control and Prevention
CFR	Code of Federal Regulations
cGMP	current Good Manufacturing Practice
CI	confidence interval
CMI	cell-mediated immunity
CoA	certificate of analysis
COPD	chronic obstructive pulmonary disease
eCRF	electronic case report form
ELISA	enzyme-linked immunosorbent assay
ELISPOT	enzyme-linked immunoSpot
eTMF	electronic Trial Master File
FACS	fluorescence-activated cell sorting
FDA	Food and Drug Administration
FTIH	first time in human
GCP	Good Clinical Practice
GLP	Good Laboratory Practice
HA	hemagglutinin
HAI	hemagglutination inhibition
HbsAg	hepatitis B surface antigen
HBV	hepatitis B virus
HCV	hepatitis C virus
HIV	human immunodeficiency virus
HRPO	Human Research Protection Office
IB	Investigator's Brochure
ICF	Informed Consent Form
ICH	International Conference on Harmonisation
ICS	intracellular cytokine staining
IEC	Independent or Institutional Ethics Committee
IgA	immunoglobulin A
IgG	immunoglobulin G
IN	intranasal(ly)
IND	Investigational New Drug Application
IP	investigational product
IRB	Institutional Review Board

IUD	intrauterine device
LAR	Legal Authorized Representative
M2SR	M 2-deficient S ingle R eplication vaccine
MAD	mucosal atomization device
MedDRA®	Medical Dictionary for Regulatory Activities
mL	milliliter
mM	millimolar
MMWR	Morbidity and Mortality Weekly Report
MN	microneutralization
MNT	microneutralization test
N	number (typically refers to subjects)
NA	neuraminidase
NAI	neuraminidase inhibition assay
NSAID	nonsteroidal anti-inflammatory drug
OTC	over the counter
PBMC	peripheral blood mononuclear cell
PE	physical exam
PCR	polymerase chain reaction
PI	Principal Investigator
PP	Per-protocol Set
PT	Preferred Term
QIV	quadrivalent influenza vaccine
qRT-PCR	real-time quantitative reverse transcription PCR
RT-PCR	reverse transcription polymerase chain reaction
SAE	serious adverse event
SAP	Statistical Analysis Plan
SE	standard error
SRC	Safety Review Committee
SPG-NaCl	sucrose phosphate glutamate with sodium chloride
SOC	System Organ Class
SOP	Standard Operating Procedure
SS	Safety Set
SUSAR	suspected unexpected serious adverse reaction
TCID	50% tissue culture infective dose
TEAE	treatment-emergent adverse event
TIV	trivalent influenza vaccine
US DoD	United States Department of Defense
US	United States
VE	vaccine effectiveness

Definitions of Terms

Baseline	Day of vaccine/placebo administration; typically last measurement taken prior to initiating treatment, determined at the record, not the visit level.
BMI	Weight in kilogram divided by the square of height in meters

STUDY ADMINISTRATIVE STRUCTURE AND INVESTIGATORS

Sponsor: FluGen Corporation
[name] USA
Funded by: United States Department of Defense (DoD)

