SAEs occurring at any time during the study will be recorded. Administration site and solicited AEs will be recorded through 7 days after each vaccination (Days 8 and 29) and unsolicited AEs will be recorded through 28 days after the last vaccination (Day 57). An SRC, comprised at a minimum of two independent physicians experienced in vaccine

research and a biostatistician, will be available to review safety data at specified time points and as needed.

Based on the safety reviews, an intermediate or lower dose may be chosen to replace the planned dose for a dose cohort. If a lower or intermediate dose is chosen that dose will be used for an entire dose cohort. Should dosing be delayed for safety review or enrollment issues, subjects may receive their second dose at a time later than defined in the proposed dosing window.

While safety and tolerability are the primary objectives, this clinical study is also designed to assess the immune response to one and two doses of each of the investigational vaccines at each of the designated dose levels. Immunogenicity will be assessed by measuring serum antibody responses by hemagglutination inhibition (HAI) and/or microneutralization (MN) assay. Additional immune parameters will be assessed including mucosal antibody titers and cell-mediated immunity. Subjects will be pre-screened, under a site-specific Informed Consent Form (ICF), to avoid enrollment of individuals with high MN titers ($> 1:20$) against the target component (A/Singapore/INFIMH-16-0019/2016 [H3N2]).

Study Conduct

After subjects have signed an informed consent and have met the inclusion /exclusion criteria, healthy adults will receive a single administration of the IP (active M2SR or placebo) delivered intranasally as a liquid formulation. The Phase 1 and Phase 2a trials in adults and the ongoing Phase 1 trial in adolescents have demonstrated that a single dose of Bris10 M2SR at 10^8 TCID₅₀ with and without a subsequent administration of a live, replicating influenza virus is generally safe and well tolerated with no shedding of infectious vaccine virus. Hence, the study will be conducted in an outpatient setting and with safety reviews as shown in [Table 2](#) and summarized here:

1. Deliver first dose to sentinel group 1 on Day 1. Lead PI reviews AEs through 3 days post-administration of first dose (Day 4), confirms that no halting rules have been met, and communicates this to the Sponsor.

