Vaccination of subjects will be suspended until after review of safety data by the SRC if any of the following halting rules are met:

1. One or more subjects experience a Grade 4 AE, vital sign or laboratory AE that cannot be clearly attributed to another cause.
2. Three or more subjects within a single sentinel group or ten or more subjects within the expansion group experience the same Grade 3 AE, vital sign or laboratory AE that cannot be clearly attributed to another cause.
3. One or more subjects experiences a SAE assessed as related to IP.

4. One or more subjects has laryngospasm, bronchospasm, or anaphylaxis associated with the study product within 72 hours of product administration.

Any AE or SAE that falls into the above criteria for suspending or terminating the study (including the occurrence of *any* Grade 3 AE, vital sign or laboratory AE that cannot be clearly attributed to another cause) must be reported by the investigator to the Sponsor *immediately (within 24 hours)*.

In the case of halting rules being met, the SRC will be convened as quickly as possible. After review of the safety data the SRC will make a recommendation to the Sponsor whether to resume, suspend or terminate the study. The Sponsor will communicate a decision to suspend or terminate the study to the Investigators.

Subsequent review of serious, unexpected, and related AEs by the Medical Monitor, SRC, IRB, the Sponsor(s), or the FDA or relevant local regulatory authorities may also result in suspension of further trial interventions/administration of study product at a site. The FDA and study Sponsor(s) retain the authority to suspend additional enrollment and study interventions/administration of study product for the entire study, as applicable.

Safety Parameters

Visual assessment of the nose on the day of IP administration (pre-dose, 5 minutes post-dose and at 30 minutes post-dose) and at follow-up assessments along with exam of throat and lungs on Patient Days 8, 29, 36, 57 and 209 will be part of a limited physical exam. Note: Appropriate medical treatment and supervision must be available to manage possible anaphylactic reactions following administration of the vaccine.

Clinical pathology will be evaluated at screen, Day 1 pre-dose, Day 8, Day 29 pre-dose and Day 36 and at additional time points as judged by the Investigator for safety evaluation.

Unsolicited local and systemic adverse events for 28 days post-dose.

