5.7. Dose and Administration

5.7.1. Vaccine

A rationale for the doses of vaccine selected in this study is provided in [Section 3.5.2](#).

Subjects will be randomly and sequentially assigned, according to the randomization schedule and in a blinded fashion, to one of 3 IP treatments: i.e., vaccine or placebo.

Each vaccine and placebo dose will be filled into a sterile 1 mL polypropylene syringe that is fitted with a Teleflex MAD301 sprayer for intranasal delivery ([Figure 2](#)) by the unblinded pharmacist or designee.

Figure 2: Image of the MAD301 Sprayer Device Fitted to a Syringe

To fill the syringe, the contents are drawn into the syringe barrel via an 18-gauge needle. The needle is removed and replaced with the MAD301 sprayer via a Luer lock fitting. The spray device

is then primed. Further details for filling and actuating the spray device are provided in the Pharmacy Manual. The pharmacist or designee will wrap an opaque label completely around the circumference of the syringe barrel to conceal any color of the liquid contents and will use an indelible marker to record the subject's ID on the label. The clinical staff credentialed to administer vaccines will then use the masked, filled spray device to administer the dose (active or placebo) intranasally to the subject.

For delivery, on each of Days 1 and 29, subjects will receive a single intranasal dose of vaccine (or placebo) via a MAD301 spray device. Subjects will be in a semi-recumbent position and receive approximately two administrations of ~50% volume per nasal cavity by employing 2 spray devices. Devices will be weighed pre- and post-dose to allow calculation of dose eliminated from the devices. Subjects will remain semi-recumbent and under observation for thirty (30) minutes and will not be allowed to blow their noses, eat, or drink during this time; any deviations are captured in the source documents and reported to the study monitor/Clinical Project Manager.

Any deviation from the dose defined in the protocol must be documented on source and in the eCRF system.

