6.1.2.7. Day 57 (28 days \pm 7 days after second dose)

- Perform limited physical examination
- Vital signs (blood pressure, heart rate, and temperature)
- Nasal swab into buffer for mucosal IgA and virus shedding
- Collect blood sample for humoral immunogenicity assays (MNT and other serum assays)
- Collect blood sample (PBMC) for cellular immunogenicity assays (ELISpot) – only by select sites
- Record concomitant therapy/AEs/SAEs

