6.1.2.8. Day 209 (180 days \pm 14 days after second dose)- on-site visit

- Perform limited physical examination
- Vital signs (blood pressure, heart rate, and temperature)
- Nasal swab into buffer for mucosal IgA and virus shedding
- Collect blood sample for humoral immunogenicity assays (MNT and other serum assays)
- Record SAEs

Due to the COVID-19 pandemic, local governments may issue stay-at-home orders which prevent centers from conducting on-site Day 209 visits. This protocol allows for the Day 209 visit to be a follow-up phone call focusing on the following safety points:

- Has the subject received any licensed vaccines since Day 1 of the trial?
- Has the subject received any investigational product (other than study IMP/placebo) since Day 1?
- Has the subject had any SAEs or medically attended AEs since the last contact with the site?

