6.2.3. Adverse Events

Adverse events will be monitored continuously from first administration of IP treatment until study Day 57. At regular intervals during the study, subjects will be asked non-leading questions to determine the occurrence of any AEs. All AEs reported spontaneously during the course of the study will be recorded as well. Solicited and unsolicited signs and symptoms will be reported as AEs after review by the Investigator or designee, either separately using the corresponding Medical Dictionary for Regulatory Activities (MedDRA) terminology of the sign or symptom or combined using the appropriate term. For example, a subject who experiences dysuria with blood, WBCs, and bacteria in the urine would be recorded as having a urinary tract infection.

For detailed definitions and reporting procedures of AEs, see [Section 9](#).

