AE/symptom. Therefore, as a secondary presentation, subjects with 3 or more concurrent unrelated AEs of cough, runny nose/rhinorrhea, sneezing, sore throat, itchy throat, itchy eyes, congestion, nasal irritation, hoarseness, headache, body aches/myalgia, tiredness/fatigue, malaise, and fever will have those AEs grouped as URI. This will simplify presentation of the data and is consistent with the protocol.

To facilitate the above reporting standard a total of 15 different AE Preferred Terms (Arthralgia, Cough, Fatigue, Headache, Malaise, Myalgia, Nasal congestion, Nasal discomfort, Nasopharyngitis, Oropharyngeal pain, Paranasal sinus discomfort, Pyrexia, Rhinorrhea, Sinus congestion, or Throat irritation) were considered for contribution to a syndromic diagnosis of URI. Subjects who reported symptoms that resulted in coding of 3 or more of these PTs on a given day, assessed by the Investigator as unrelated to the vaccine, were reported as URI. The severity of the URI was reported as the worst severity of the qualifying AEs considering only days when 3 or more terms were reported. AEs already reported by the Investigator as a URTI were not included in the URI data display.

Targeted physical examinations were conducted throughout the study. PE findings recorded as clinically significant, severe, or life threatening were recorded as AEs. Investigators used their judgement regarding reporting of additional PE findings as AEs.

Clinical laboratory results marked as clinically significant by the Investigator were captured as AEs.

AE's with start dates prior to the first IP administration will be included in the listings, but not in the summaries.

Treatment-emergent AEs (TEAE) are AEs with start dates between administration of the first IP and last IP administration + 30 days. However, if an AE is related to IP then there is no upper bound on the start date. Thus, treatment related TEAEs may have start dates beyond 30 days post IP administration.

All AEs will be coded based on MedDRA (V20.0).

Where provided in Protocol Appendix 1, AEs will be graded according to the Vital Sign and Systemic Toxicity Assessments.

N (%) of subjects with at least one TEAE and N (%) of subjects with at least one treatment-related treatment-emergent AE (TRAE) will be summarized. TEAE and TRAE by worst severity will be summarized. Note that the protocol uses the term "vaccine associated" AEs, but the eCRF collects AEs as related, not related.

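### The protocol sets unsolicited AE recording at 28 days after the last dose, but the last scheduled general AE inquiry may fall on day 21, and the SAP uses two other periods

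*Protocol*

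**What the plan says.** - **Stated follow-up.** The synopsis (Overview of Study Design) and protocol 3.1 both say that "unsolicited AEs will be recorded through 28 days after the last vaccination (Day 57", closing the bracket there. The synopsis list of safety parameters repeats the length: "Unsolicited local and systemic adverse events for 28 days post-dose".
- **End of monitoring.** Protocol 6.2.3 says "Adverse events will be monitored continuously from first administration of IP treatment until study Day 57". Protocol 9.1 uses the same end point.
- **Visit window.** The heading of protocol 6.1.2.7 gives the visit as "Day 57 (28 days \pm 7 days after second dose", and its task list includes "Record concomitant therapy/AEs/SAEs". Table 3 shows the same window, counted with the second dosing day as day 1.
- **After that visit.** The general AE row of Table 3 has no entry at Day 209. The on-site list in 6.1.2.8 records SAEs. The telephone alternative asks "Has the subject had any SAEs or medically attended AEs since the last contact with the site".
- **SAP 9.2.** AE recording is described as running to Day 57 plus a further 28 days. The analysis window is different: "Treatment-emergent AEs (TEAE) are AEs with start dates between administration of the first IP and last IP administration + 30 days". AEs judged related to IP have no upper date limit.

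**The concern.** Safety is the primary objective, and this is the first human study of Sing2016 M2SR, so the absolute AE percentages matter even though nothing is tested. The schedule does not guarantee the stated 28 days of active inquiry after dose 2. A fully compliant visit on day 21 ends scheduled general AE questioning a week early, and nothing requires a further contact at day 28. Follow-up length then differs between subjects without being shown. The SAP summarises AEs on the Safety Set and imputes nothing (8.5), so a subject last asked on day 21 counts in the denominator like one asked on day 35. The SAP's own periods fit neither the stated 28 days nor the visit window.

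**Working it through.** **1. The plan's own figure.** Protocol 5.7.1 gives the dosing days: "For delivery, on each of Days 1 and 29, subjects will receive a single intranasal dose of vaccine (or placebo". With dose 2 on Day 29, 29 + 28 = Day 57. The stated figure reproduces.

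**2. When V07 may fall.** From 6.1.2.7: 28 - 7 = 21 and 28 + 7 = 35 days after dose 2. From Table 3: post-dose-2 Day 29 ± 7 is Day 22 to Day 36. With the dosing day as day 1, subtract 1, which gives 21 to 35 days. The two sources agree.

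**3. Whether a later scheduled contact fills the gap.** Day 209 does not, because it takes SAEs and medically attended AEs. The extra influenza contacts (6.1.3; Table 3, footnote 19) depend on local influenza activity and concern influenza symptoms. The last is at Day 50 ± 2, so at the latest Day 52, which is 52 - 29 = 23 days after a dose 2 given on Day 29.

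**4. Size of the gap.** For a visit v days after dose 2, the shortfall is max(0, 28 - v)/28 against the protocol and max(0, 30 - v)/30 against the SAP's treatment-emergent window.

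| V07, days after dose 2 | Shortfall against 28 days | Shortfall against 30 days |
|---|---|---|
| 21 | 7/28 = 25% | 9/30 = 30% |
| 28 | 0 | 2/30 = 6.7% |
| 35 | 0 | 0 |

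Even an on-time visit leaves days 29 and 30 of the SAP window without scheduled inquiry. Only later visits reach them.

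**5. The SAP's recording period.** 57 + 28 = Day 85, and 85 - 29 = 56 days after a nominal dose 2. No scheduled visit collects general AEs that far out. The documents thus give three lengths after dose 2: 28, 30 and 56 days.

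**6. The Day 57 label.** Dose 2 may be given at Day 29 ± 7, so as late as Day 36. Read as a calendar day, Day 57 is then 57 - 36 = 21 days after dose 2. Read as tied to dose 2, it means 36 + 28 = Day 64. Protocol 6.2.3 and 9.1 do not say which.

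**7. Share of subjects affected.** The documents give no distribution of visit dates, so the share seen before day 28 could be anything from 0 to 100%, and the mean loss anything from 0 to 7 days. As an illustration only, suppose visits were spread evenly over the 15 permitted days. Then 7/15 = 47% would be seen early, with a mean loss of (1 + 2 + ... + 7)/15 = 28/15 = 1.9 days (6.7% of 28).

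**The case against.** A reader might infer that AEs in the last week are never collected, or that V07 closes collection. The documents do not support this. No section says that collection closes at the visit. Protocol 6.2.3 has spontaneously reported AEs recorded during the study, 9.6 requires AEs during the investigation to be documented, and 9.1 takes SAEs and medically attended events to Day 209. What is missing is scheduled questioning about the remaining, milder events.

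A reader might also infer a second gap when dose 2 is late. The protocol mostly ties Day 57 to the second dose (3.1, the contraception criteria in 4.1, 6.1.2.7, and the separate post-second-dose row of Table 3). This is an ambiguity in 6.2.3 and 9.1, not a second loss of follow-up.

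On the primary endpoint, the objection has force. It counts vaccine-associated AEs or SAEs, SAEs run to Day 209, and the SAP puts no upper date limit on related AEs. Milder related events late after dosing may be few. Having no upper limit does not create a contact, however. A related event that is mild and not volunteered is still not asked about.

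On magnitude, the illustration in step 7 counts only early visits. Under the same even spread, late visits add days that the SAP's 30-day window counts: (1 + 6 × 2)/15 = 0.87 days. The net mean shortfall against 28 days is then 1.87 - 0.87 = 1.0 day (3.6%). That is fair for average follow-up, but it does not restore the missing days in subjects seen early.

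Finally, the SAP is dated 28 July 2020, writes of AE collection in the past tense and reports enrolment already halted. A new visit window may come too late for this trial. The SAP changes would not.

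**Conclusion.** The point stands in limited form. The protocol states 28 days, permits the last scheduled general inquiry at 21, and the SAP analyses 30 and describes 56. The worst case for one subject is 7 of 28 days (25%) without scheduled solicitation of non-serious AEs that do not lead to medical attention. A subject seen on day 28 or later loses nothing against the protocol's statement. That V07 is the last such inquiry is read from Table 3 and the visit lists, not from an explicit rule.

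The number of subjects affected is unknown. The AE percentages can only be understated by this, probably slightly. With blinded staff and the same visit rules in every arm, comparisons between arms should be little affected. The case for acting rests on safety being the primary objective, the conflict between the stated periods, and the low cost of correction.

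**What to change.** 1. **Protocol Table 3 and 6.1.2.7.** Set V07 to 28 days (-0/+7) after dose 2. Alternatively, keep ±7 days for blood and swabs and make the scripted call already used on Days 4 and 32 at day 28 after dose 2 for anyone seen earlier. The protocol already protects the diary in a similar way (6.2.1.6): subjects seen on Day 35 get a pre-addressed envelope to complete and return it.
2. **Protocol 6.2.3 and 9.1.** Give the end of AE monitoring as 28 days after the last dose, in place of a bare study day.
3. **SAP 9.2.** State the same recording period in place of Day 57 plus 28 days. End the treatment-emergent window for AEs not judged related at 28 days after the last dose.
4. **AE overview table.** Add a row, by arm, with the number of subjects whose last AE contact came before day 28 after their last dose.

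If visits are already complete, items 3 and 4 still apply and need only recorded visit dates. The cost is one short call for subjects seen early, or slightly later visits, plus wording changes and one table row.
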